9.3.2. Shifts in CTCAE Grade

Quantitative laboratory tests will be assigned grades based on CTCAE Version 4.03, where applicable. Shifts in CTCAE grade of laboratory tests will be presented from OLE baseline to worst post OLE baseline value, last post OLE baseline value, best post OLE baseline value, and at each post OLE baseline visit. Summaries will present the number and percentage of subjects with shifts in laboratory grade. Denominators for percentages will be the number of subjects with non-missing data at the specific assessment and OLE baseline.

In addition, the number and percent of subjects with a lab value with CTCAE Grade ≥ 3 and the number and percent of subjects with a CTCAE shift of ≥ 2 grades will be presented.

Where applicable, if the quantitative criteria for grading are equivalent for two grades, only differentiated by clinical interventions, the clinical intervention will be ignored and the highest CTCAE grade will be used.

9.3.3. Shifts in Normal Range

In addition, for laboratory tests that cannot be graded via CTCAE, shift tables (i.e., low-normal-high at baseline versus low-normal-high at post-baseline visit in a 3-by-3 contingency table) from OLE baseline to worst post OLE baseline value, last post OLE baseline value and at each post OLE baseline visit will be presented. Denominators for percentages will be the number of subjects with non-missing data at the specific assessment and baseline.

9.3.4. Pregnancy Testing and Urinalysis Dipstick

Pregnancy test results and urinalysis dipstick results will not be summarized and will be provided in a by-subject data listing.

9.4. Weight and BMI

Weight (kg), BMI (kg/m^2), and mBMI ($\text{kg}/\text{m}^2 \text{ g/L}$), defined as a subject's weight (kg) \div subjects squared height (meters) \times serum albumin (g/L), will be summarized using descriptive statistics at NEOD001 baseline, OLE baseline, at each post NEOD001 baseline visit, and at each post OLE baseline visit. In addition, changes and percent changes from NEOD001 and OLE baselines will be presented.

9.5. Vital Signs

Vital sign parameters including temperature (C), systolic and diastolic pressure (mmHg), pulse (beats/min), and respiratory rate (breaths/min) will be presented in a data listing. Method of collection will be provided in the listing; however, summaries will be generated without regard to the method of collection. Summaries of vital sign parameter results, change from NEOD001 baseline, change from OLE baseline, percent change from NEOD001 baseline, and percent change from OLE baseline, will be summarized using descriptive statistics at baseline and at each post-baseline visit. In addition, change and percent change from baseline will be presented from pre-dose to post-dose at infusion visit.

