Due to the limited number of infusion-site related reactions reported to date, premedication of subjects prior to the start of NEOD001 infusion is not required in the NEOD001-OLE001, NEOD001-201, and NEOD001-OLE251 protocols. As of 30 September 2016, 221 subjects had been dosed in the 4 completed or ongoing studies. In Study NEOD001-CL002 (VITAL), 129 subjects received a total of 534 infusions of blinded study drug (24 mg/kg NEOD001 plus standard of care or placebo plus standard of care). In Study NEOD001-201 (PRONTO), 23 subjects received a total of 51 infusions of blinded study drug (24 mg/kg NEOD001 or placebo). In Study NEOD001-001, 69 subjects received 994 infusions of NEOD001 (up to doses of 24 mg/kg). In the completed Study NEOD001-001, 9 infusion-site reactions were reported (6 subjects) and most (n=7; 78%) were classified as Grade 1. As noted above, 1 subject in the ongoing Study NEOD001-201 experienced an event of vasovagal syncope (characterized by bradycardia, hypotension, and syncope). Another aspect of safety monitoring in studies of NEOD001 has been a required postinfusion observation time ranging from 60 to 120 minutes. In addition to this study, Studies NEOD001-201 and NEOD001-OLE251 allow for flexibility in monitoring time if no reactions are seen after the first 2 infusions, as described in Section 5.3.

Based on the data available to date, NEOD001 has been well tolerated as single-agent therapy in subjects with AL amyloidosis and no clinically significant safety signals have been identified. See the current NEOD001 Investigator's Brochure for detailed clinical information.

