3.2 STUDY ENDPOINTS

3.2.1 Primary

- Assessment of the safety and tolerability of NEOD001 as assessed by vital signs, duration of therapy, 12-lead electrocardiograms (ECGs), routine laboratory assessments, and frequency and severity of AEs

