5.4 DOSE ADJUSTMENTS

5.4.1 Withholding of Study Drug

Subjects with symptomatic orthostatic hypotension or systolic BP <85 mmHg, which in the medical judgment of the Investigator would interfere with subject's ability to safely receive treatment, will have study drug withheld.

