2.3. Study Endpoints

2.3.1. Primary Endpoints

The primary study endpoints are the frequency and severity of AEs, changes in laboratory assessments from OLE baseline, and change in vital signs and 12-lead ECGs from NEOD001 baseline and OLE baseline.

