9.6. Electrocardiograms

ECGs measurements will be made in triplicate, 5 to 10 minutes apart and assessed by a central reader. For summary purposes, the mean of the three measurements will be used. ECG parameters including, time between 2 consecutive R waves [RR], PR interval, QRS duration, QT (uncorrected) interval, QT interval corrected by the Bazett's formula [QTcB], and QT interval corrected by the Fridericia's formula [QTcF], will be summarized using descriptive statistics will be presented for observed values, change from NEOD001 baseline, change from OLE baseline, at each NEOD001 post-baseline time point, and at each OLE post-baseline time point.

A categorical summary of the following abnormal maximum mean triplicate QTcF values will be presented: >450 msec, >480 msec, and >500 msec. Change from NEOD001 baseline and OLE baseline summaries will also be presented for measurements that represent a change from baseline >30 msec and >60 msec. Three separate listings for those subjects with any QTcF >450 msec or a QTcF change from either baseline >30 msec, any QTcF >480 msec or a QTcF change from either baseline >30 msec, and any QTcF >500 msec or a QTcF change from baseline >60 msec will be presented. The observation(s) meeting criteria for inclusion will be flagged in the listing.

Overall interpretation results for ECGs and the investigator interpretation results are collected as normal, abnormal not clinically significant, and abnormal clinically significant. Subjects whose interpretation shifts from normal to abnormal clinically significant or not clinically significant will be listed separately including description of the abnormality and any associated comments.

All ECG results will be presented in by-subject data listings.

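### SAP 9.5 sets no threshold, worst-value or flagged summary for vital signs, so a measured fall around an infusion is counted by subject only if it was reported as an adverse event

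*SAP*

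**What the plan says.** Both documents make vital signs primary. Protocol 3.2.1 lists "Assessment of the safety and tolerability of NEOD001 as assessed by vital signs, duration of therapy" among its measures, and SAP 2.3.1 names "change in vital signs and 12-lead ECGs from NEOD001 baseline and OLE baseline".

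SAP 9.5 plans three displays:

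- A listing: "pulse (beats/min), and respiratory rate (breaths/min) will be presented in a data listing".
- Summaries of values, changes and percent changes, of which the last is worded "percent change from OLE baseline, will be summarized using descriptive statistics at baseline and at each post-baseline visit". Under SAP 4.1 these statistics are n, mean, SD, median, quartiles, minimum and maximum.
- An infusion-day comparison: "change and percent change from baseline will be presented from pre-dose to post-dose at infusion visit".

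Readings are frequent. Table 1, footnote 8, of the protocol asks for them before dosing, at end of infusion and 60 minutes later at every infusion. At Month 1 it adds a reading halfway through and one at 30 minutes.

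Protocol 5.4.1 already contains a numeric blood pressure limit: "Subjects with symptomatic orthostatic hypotension or systolic BP <85 mmHg", subject to the investigator's judgment. No SAP table uses it. For ECGs, by contrast, SAP 9.6 says: "A categorical summary of the following abnormal maximum mean triplicate QTcF values will be presented".

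**The concern.** The harm these readings are meant to catch is a large fall in one person at one infusion. The protocol shows the type of event: in 1.3.2, one subject in another study, NEOD001-201, on blinded drug, "experienced an event of vasovagal syncope (characterized by bradycardia, hypotension, and syncope". A safety report on long-term infusion should be able to say how many subjects ever had such a fall, and at how many infusions.

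By-visit summaries describe the group at each visit and do not link a subject's visits, so that number cannot be built up from them. This carries weight here because SAP 8 and SAP 11 reduce efficacy to listings. The safety tables are then most of what the study will report in summary form.

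**Working it through.** The documents give no planned figure on this point (sample size is stated as not applicable) and no extension vital-sign data. The check sets the sections side by side, with illustrative arithmetic under stated assumptions.

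**1. What each safety domain receives**

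| Domain | Count by subject against a limit, grade or range | Worst value | Listing |
|---|---|---|---|
| Laboratory (SAP 9.3) | CTCAE Grade ≥3, shift of ≥2 grades, or normal-range shift | Yes | Separate listing for Grade 3 or 4 |
| ECG (SAP 9.6) | QTcF >450, >480, >500 msec; change >30, >60 msec | Yes (maximum) | Qualifying observations flagged |
| Vital signs (SAP 9.5) | None | None | All values, no flag |

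**2. Can the by-visit statistics supply the count?**

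Assume that k of N subjects with data at a visit have a fall of D mmHg in systolic pressure and nobody else changes.

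Shift in mean change = −k × D / N, and proportion affected = k / N.

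Inputs: N = 70 (protocol 3.3, approximate) down to 40 (assumed attrition); D = 30 to 40 mmHg (assumed); k = 1 or 3 (assumed).

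- One subject: −30/70 = −0.43 to −40/40 = −1.00 mmHg.
- Three subjects: −90/70 = −1.29 to −120/40 = −3.00 mmHg. With N = 70 and D = 40 the shift is −120/70 = −1.71 mmHg.
- For scale, with an assumed SD of change of 12 to 15 mmHg, the standard error at N = 70 is 12/√70 = 1.43 to 15/√70 = 1.79 mmHg.
- Proportion affected: 1/70 = 1.4% to 3/40 = 7.5%. This is well below 25%, so the lower quartile and the median hardly move.
- The minimum does show the largest fall at that visit. It cannot show whether one subject or three fell.

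Across visits, take seven equal falls at seven different visits. If seven subjects had one each, 7/70 = 10.0% were affected. If one subject had all seven, 1/70 = 1.4% were. Under the same assumption the by-visit change tables are identical in the two cases.

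**3. Where do the first-infusion readings go?**

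- SAP 4.1 makes the day of the first extension dose Day 1.
- SAP Table 4 takes OLE Baseline from before that dose and opens the OLE Month 1 window on Day 2.
- Readings taken halfway through, at the end, and 30 and 60 minutes after the Month 1-Day 1 infusion are on Day 1 but after the dose. They are neither baseline nor in any OLE window.
- SAP Table 2 counts from the start of NEOD001 therapy. It may place them in a window for subjects with a gap of 60 days or less between studies. For a longer gap, SAP 2.2.4.1 restarts the clock at the extension dose, and the same hole appears.
- That leaves the pre-dose to post-dose sentence in SAP 9.5. It does not say which post-dose reading is used and does not name the halfway reading.

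**4. What do the adverse event tables add?**

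SAP 9.2.3, 9.2.6 and 9.2.9 count subjects with reported events. Under protocol 7.1 a new abnormality in physiological testing becomes an adverse event when judged clinically significant. Protocol 7.4.3 says progression of organ dysfunction should generally not be reported as a specific event. Protocol 1.1 lists the autonomic nervous system among the organs involved, so a low reading could be put down to disease. In SAP Appendix 5, hypotension counts toward anaphylactic reaction only together with a Group B or C term. A measured fall that is not reported is counted in none of these tables.

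**The case against.** A reader might infer that infusion-related hypotension or bradycardia appears in no table. The documents do not support that. If reported, it is counted by subject over the whole study in several tables: all treatment-emergent events by SOC and PT, those leading to an interrupted or held dose, infusion-associated events, and events on the infusion day. The syncope in protocol 1.3.2 was itself such an event and would be tabulated. Protocol 6.3.2 has clinically important pressure changes re-measured at once, which makes reporting of symptomatic falls likely. This stands, and it confines the gap to measured falls that were not reported.

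Nor are large falls wholly hidden. The minimum of the pre-dose to post-dose change would show an extreme one, and every value is listed, so a count by hand is possible. That also stands, but a reader should not have to build a primary safety count from listings.

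SAP 9.5 broadly follows protocol 8.3, which asks only for descriptive statistics and change from baseline. So this is not a departure from protocol. SAP 11 does, however, state that the SAP adds safety analyses.

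Finally, the 85 mmHg figure is a withholding criterion, not an endpoint. Inclusion criterion 4 admits a systolic pressure of 90 mmHg, from which a fall of 6 mmHg gives 84. The absolute category alone would therefore mix small and large falls. That is a reason to show it beside change categories.

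**Conclusion.** The gap is real and narrow. For a primary endpoint measured around every infusion, no table counts the subjects with a measured fall in blood pressure or heart rate unless an adverse event was reported. The first-infusion readings are the least well covered. This follows from the text of SAP 4.1, 4.6.2 and 9.5 and needs no assumption. The arithmetic only illustrates why means, quartiles and minima cannot stand in for a count; it rests on assumed falls, numbers at a visit and SD.

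Two further inferences should be avoided. The syncope came from another, blinded study, so it shows a type of event and says nothing about its rate here. The documents also give no rate of large falls per infusion, so no number of affected subjects can be projected. The nearest figures are 9 infusion-site reactions in 6 of 69 parent-study subjects over 994 infusions. They concern a different event, and more events than subjects means some subjects had more than one. A projection that treats infusions as independent and gives every subject all 36 would not be supported.

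This is a cheap improvement to the study's main safety question, not a flaw that invalidates the analysis.

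**What to change.** Add to SAP 9.5 one table for the OLE Safety Population, giving the number and percent of subjects and of infusions with:

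- any systolic pressure below 85 mmHg after infusion start when the same-day pre-dose value was 85 mmHg or higher, using the protocol's figure purely as a reporting category;
- a fall in systolic pressure from the same-day pre-dose value beyond limits that the sponsor prespecifies;
- the same for heart rate.

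State the denominators: for example, infusions with a pre-dose reading and at least one reading after the start. Name every time point that counts: the Month 1 halfway reading, end of infusion, 30 minutes at Month 1, and 60 minutes. Say explicitly that Month 1-Day 1 is included. Flag qualifying subjects and readings in the existing listing.

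The cost is SAP wording, one table and a flag, all from data already collected. The downside is that subjects with low entry pressure may meet the absolute category after a small fall, so it should be read with the change categories. No dosing or withholding rule is touched.

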9.6. Electrocardiograms

ECGs measurements will be made in triplicate, 5 to 10 minutes apart and assessed by a central reader. For summary purposes, the mean of the three measurements will be used. ECG parameters including, time between 2 consecutive R waves [RR], PR interval, QRS duration, QT (uncorrected) interval, QT interval corrected by the Bazett's formula [QTcB], and QT interval corrected by the Fridericia's formula [QTcF], will be summarized using descriptive statistics will be presented for observed values, change from NEOD001 baseline, change from OLE baseline, at each NEOD001 post-baseline time point, and at each OLE post-baseline time point.

A categorical summary of the following abnormal maximum mean triplicate QTcF values will be presented: >450 msec, >480 msec, and >500 msec. Change from NEOD001 baseline and OLE baseline summaries will also be presented for measurements that represent a change from baseline >30 msec and >60 msec. Three separate listings for those subjects with any QTcF >450 msec or a QTcF change from either baseline >30 msec, any QTcF >480 msec or a QTcF change from either baseline >30 msec, and any QTcF >500 msec or a QTcF change from baseline >60 msec will be presented. The observation(s) meeting criteria for inclusion will be flagged in the listing.

Overall interpretation results for ECGs and the investigator interpretation results are collected as normal, abnormal not clinically significant, and abnormal clinically significant. Subjects whose interpretation shifts from normal to abnormal clinically significant or not clinically significant will be listed separately including description of the abnormality and any associated comments.

All ECG results will be presented in by-subject data listings.

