9.3. Clinical Laboratory Evaluations

Laboratory parameters will be presented in Système International (SI) units.

Local laboratories were used during the original parent study NEOD001-001. A central laboratory (Covance Central Laboratory Services) was used for this open-label extension, NEOD001-OLE001. Data from the local and central labs will not be pooled. Summaries will only present data from the central laboratory for OLE Safety Population.

All clinical laboratory data will be presented in by-subject data listings. In addition, separate listings will be presented for any subject with a post OLE baseline CTCAE Grade 3 or 4 laboratory value.

The following normal ranges will be used where not provided in the central laboratory data:

- INR Upper Limit of Normal (ULN) = 1.1
- eGFR LLN = 90 mL/min/1.73m²

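### SAP 9.6 does not separate new QTcF threshold crossings from prolongation already present at baseline, and no planned summary table does so

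*SAP*

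**What the plan says.** **QTcF (SAP 9.6).** The threshold table is specified in one sentence: "A categorical summary of the following abnormal maximum mean triplicate QTcF values will be presented", the cut-offs being >450, >480 and >500 msec. The section then plans summaries, from both the NEOD001 and OLE baselines, of "measurements that represent a change from baseline >30 msec and >60 msec". Three listings combine an absolute cut-off with a change criterion, the first being "any QTcF >450 msec or a QTcF change from either baseline >30 msec", and the qualifying observations are flagged. A further listing covers the overall reading: "Subjects whose interpretation shifts from normal to abnormal clinically significant or not clinically significant will be listed separately". All ECG results are also listed by subject.

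**Laboratory tests (SAP 9.3 and 9.3.2).** SAP 9.3.2 cross-tabulates CTCAE grade at OLE baseline against the worst, last, best and each-visit post-baseline grade. It adds a count, "the number and percent of subjects with a lab value with CTCAE Grade ≥ 3", and a count of shifts of at least two grades. SAP 9.3 says that "separate listings will be presented for any subject with a post OLE baseline CTCAE Grade 3 or 4 laboratory value".

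**Context.** SAP 2.3.1 makes change in ECGs from both baselines part of the primary endpoint. The protocol synopsis gives no control group. Protocol 4.1 requires at least 9 months of earlier treatment in the parent study.

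**The concern.** The threshold sentence leaves three things open: whether the baseline reading can itself be the maximum, whether the maximum runs over the OLE alone or over parent study and OLE together, and which safety population is the denominator. Even if these were settled, the count takes no account of where a subject started. Someone who entered above 450 msec and stayed there, or improved while remaining above it, is counted in the same row as someone who crossed 450 msec during the study.

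This can happen because the criteria in Protocol 4.1 and 4.2 set no QTc ceiling. Exclusion 1 is a judgement about new or clinically significant findings that preclude treatment or participation.

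With no control arm, each subject's baseline is the only comparator. A threshold table that does not refer to it does not measure the change that SAP 2.3.1 names as an endpoint, and its percentages may be read as new prolongation.

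**Working it through.** The plan states no expected QTcF abnormality rate, so there is no figure to reproduce. The check is first a reading of the planned outputs, then an illustration.

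**1. Do the planned summary tables separate new from pre-existing?** Take two constructed subjects, with the same value at both baselines.

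| Baseline → maximum post-baseline | Change | Threshold rows entered | Change rows entered |
|---|---|---|---|
| 480 → 505 msec | 505 − 480 = 25 | >450, >480, >500 | none (25 is below 30) |
| 505 → 505 msec | 0 | >450, >480, >500 | none |

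The first subject newly exceeds both 480 and 500 msec; the second is unchanged. The two planned QTcF categorical summaries treat them identically. The interpretation-shift listing does not fill the gap, because it uses the overall ECG reading and starts only from normal. Both subjects appear, flagged, in the absolute-threshold listings, so they can be told apart by looking up their baselines by hand.

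**2. Illustrative size.** Let p be the share above a cut-off at baseline and q the new incidence among the rest. If baseline-abnormal subjects are all counted:

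- share shown in the table = p + (1 − p)q
- part already abnormal = p / [p + (1 − p)q]

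N = 70 comes from Protocol 3.3. Both p and q are assumptions (p 5% to 40%, q 0% to 10%).

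| p | q | Table shows | Subjects | Newly abnormal | Already abnormal |
|---|---|---|---|---|---|
| 5% | 0% | 5.0% | 3.5 | 0 | 100% |
| 5% | 10% | 14.5% | 10.2 | 6.7 | 34% |
| 20% | 5% | 24.0% | 16.8 | 2.8 | 83% |
| 40% | 0% | 40.0% | 28.0 | 0 | 100% |

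For the third row: 0.20 + 0.80 × 0.05 = 0.24; 0.24 × 70 = 16.8; 0.80 × 0.05 × 70 = 2.8; 0.20 / 0.24 = 0.83. The same table percentage can therefore reflect very different amounts of new prolongation.

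**3. A separate effect: the maximum over many readings.** Protocol Table 1 schedules ECGs at Months 3 to 36 every 3 months, predose and after infusion: 12 × 2 = 24 readings, plus EOS. For a subject with true mean 440 and SD 10 msec (assumed) and independent readings, the chance of at least one value above 450 is 1 − Φ(1)^24 = 0.98. With 8 readings (4 visits) it is 1 − Φ(1)^8 = 0.75. Correlated readings would lower both. This concerns taking a maximum, not the starting value.

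**4. Laboratory count.** The Grade ≥3 count omits the post-OLE-baseline limit that the shift tables and the SAP 9.3 listing carry. The two-grade count misses moves from Grade 2 to 3 and from 3 to 4. The grade shift tables show both moves, and show baseline Grade 3 as such, test by test.

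**The case against.** The best case for the plan is that nothing is hidden. SAP 9.6 summarises observed values and changes at each time point from both baselines, summarises large changes, flags the qualifying observations and lists every ECG. With about 70 subjects, each threshold crosser can be checked individually. The study is descriptive, and SAP 9 plans no inferential safety comparison. Exclusion 1 should also keep out some of the more extreme ECG findings.

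Much of this stands, and it rules out several stronger readings that a reader might infer:

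- **That baseline abnormalities are reported as on-treatment toxicity.** The SAP gives neither count that label. It defines treatment emergence only for adverse events (SAP 9.2).
- **That a real new signal cannot be separated.** It can, from the listings; what is missing is a summary table.
- **That the laboratory count has the same defect.** The shift tables in SAP 9.3.2 already separate baseline from later grades, and the Grade 3 or 4 listing is already limited to post-baseline values.
- **That subjects abnormal at OLE baseline are counted without any drug effect.** They have already had at least 9 months of NEOD001, so the abnormality may have arisen on drug.

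A further fair objection is that a shift to the worst category does not cure the maximum effect. The subject with true mean 440 and SD 10 msec is at or below 450 at baseline with probability 0.84, and would then appear as a new crossing with probability about 0.84 × 0.98 = 0.83 under 24 independent readings.

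None of this supplies a table that relates the QTcF cut-offs to baseline.

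**Conclusion.** The point holds for QTcF as a gap in descriptive reporting. As written, the threshold table has no post-baseline limit, no stated period or population and no link to baseline, and no other planned summary table makes that link. That conclusion rests on the text alone.

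Its size is unknown. The documents give neither baseline prevalence nor new incidence; the illustration assumes both and assumes that every subject above a cut-off at baseline is counted. The laboratory part is minor. No test, error rate or sample size changes.

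**What to change.** **SAP 9.6**

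- Limit the QTcF maximum to post-baseline values, and state the period and the analysis population.
- Add a shift table from baseline QTcF category (≤450, >450–480, >480–500, >500 msec) to worst post-baseline category.
- Produce it from both the NEOD001 and OLE baselines, since the OLE baseline alone would class prolongation that arose in the parent study as pre-existing. Under SAP 2.2.4.1 the two baselines coincide for subjects with more than 60 days between last parent-study dose and first OLE dose, so a footnote should give their number.
- Note beneath the table that the worst category depends on how many readings a subject contributes.

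**SAP 9.3.2 (minor)**

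- Add the post-OLE-baseline limit to the Grade ≥3 count.
- Add a row for Grade ≥3 values worse than the OLE-baseline grade. Only the OLE baseline is usable here, because SAP 9.3 does not pool local parent-study results with central ones.

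**Cost.** A few lines of SAP text, one shift table run from two baselines and one extra laboratory row. All of it uses data already collected.
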